
4. Methods

Symptomatic paroxysmal AF patients diagnosed with HFpEF seeking emergency treatment that meet all inclusion and none of the exclusion criteria will be randomized according to E-TEAM in two groups (1:1 randomization) as follows:

Group 1: early catheter ablation within 7 days post AF-related emergency treatment using the FARAPULSE electroporation technology (n = 100)

OR

Group 2: best medical AF treatment including rhythm and rate control (n=100)

All patients will receive (direct) oral anticoagulation and heart failure treatment according to their CHA₂DS₂-VASC Score and current ESC guidelines ^{1 2}.

5. Ablation

The FARAPULSE AF ablation system represents a unique single shot ablation technology associated with a high rate of acute and durable PV isolation ¹⁴. In principle, electroporation delivers a cardiac selective ablation, thus sparing non-cardiac tissue. The endpoint of the catheter ablation procedure is defined to PVI. Therefore, this technology offers a unique beneficial profile combining a high procedural efficacy and safety.

6. Endpoints

The **primary endpoint** is a composite of cardiovascular hospitalization (worsening heart failure, acute coronary syndrome, AF/AT recurrence, cardioversions, re-ablations), death, systemic embolism, stroke (ischemic, hemorrhagic) and emergency (E) treatment for cardiovascular reasons.

Secondary endpoints are defined to safety parameters such peri-procedural complications (major bleeding requiring intervention, phrenic nerve palsy, pericardial tamponade, thromboembolic events, atrio-esophageal fistula, death) or discontinuation of AAD due to side effects and documented recurrence of AF or any atrial tachyarrhythmia lasting longer than 30 seconds between day 90 and 365 after the index procedure as well as number of nights spent in the hospital per year.

Study Design

The proposed pilot study is a prospective, randomized, single-center feasibility study, enrolling 200 patients with symptomatic paroxysmal AF. Per protocol, 100 patients will undergo a FARAPULSE electroporation PVI and 100 patients will receive standard AF medical treatment.

Prior enrollment, all patients will be informed on the risk and benefits of the PVI procedure as well as the medical treatment. In addition, particular information on the rationale of the study, including a detailed risk/benefit analysis, will be provided to all patients.

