After obtaining written informed consent and randomization, patients will be treated according to the assigned groups (FARAPULSE electroporation PVI vs. optimized medical care). Follow-Up duration is 12 months. Importantly, cross-over between both groups is strongly discouraged. **If deterioration occurs in group 2, PVI is advised.**

Risk-Benefit-Analysis

Catheter ablation of paroxysmal AF represents an invasive procedure but is linked to a lower AF recurrence rate if compared to medical treatment. Participants in Group 2 (control group) will receive best medical treatment including the option for electrical cardioversions and AAD treatment.

The novel energy source using electroporation appears to be appealing due to its potential of short procedure times and cardiomyocyte selectivity resulting in a benign safety profile. The participants in Group 1 will be scheduled to receive the ablation therapy early after the AF diagnosis (within 7 days).

In general, catheter ablation for AF is an invasive treatment associated with potential complications. Of note, as stated above electroporation appears to be associated with a very benign risk profile. General AF related complications and corresponding incidences are summarized in the following:

- Vascular access complications such as vascular damage, neural damage, hematoma, bleeding (approx. 2-3%)
- Pericardial tamponade (<1%)
- Systemic Infection (<1%)
- Thrombo-embolic complications including air embolism, transient ischemic attack and stroke (<1%)
- Pulmonary vein stenosis or occlusion (<0,5%)
- Atrio-esophageal fistula (< 1%)
- Death (< 0.1%)

All devices utilized for the ablation procedure are fully licensed, CE mark approved and are used in the clinical routine. Patients randomized to Group 2 will receive standard medication including all non-interventional options for a rhythm control strategy in the treatment of paroxysmal AF. Therefore, no patient will be exposed to a higher risk due to the participation in the E-TEAM-Trial.

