6.3 Repeat ablation

No blanking period will be utilized in this study. During the first 90 days after the index procedure any arrhythmia recurrence shall be treated conservatively, e.g. by antiarrhythmic medication and/or ECV. Of note, re-ablation is strongly discouraged within the first 3 months. At day 90 however, all AAD drugs should be stopped in the ablation group and all re-ablation afterwards will meet the primary endpoint. In case of re-ablation the patient has reached the primary endpoint. The Follow-Up visits should be continued as per protocol.

7. Participant withdrawal or termination of participation

Prior to study entry, all participants will be informed that they are free to withdraw from the study at any time and for any reason without prejudice to their future medical care by a physician or the institution. Participants are free to withdraw from participation in the study at any time upon request. The withdrawal will cause no penalty or loss of benefits, to which the patients may otherwise be entitled. The investigator may ask and document the patients' motivation.

An investigator may also terminate a patients' participation in the study if:

- Withdrawal is in the subjects' best interest.
- Subject withdraws consent.
- Subject is lost to follow up.

8. Statistical Analysis

No interim-analysis will be performed.

The following events will trigger a premature study termination:

- Occurrence of serious adverse events in more than 10% of the study population associated with the ablation procedure. Of note, re-hospitalization for cardiovascular reasons meets the primary study endpoint.
- Occurrence of any unexpected, currently unknown complication or risk (Change of Risk-Benefit Ratio).

Occurrence of >10% major procedural complications defined as cardiac tamponade, stroke/TIA, air embolism, major bleeding the study has to be stopped. Of note re-hospitalization for cardiovascular reasons meets the primary endpoint.”

9. Adverse Events

All adverse events (AEs) experienced by participants during the study, beginning with the first study related procedure and continuing through the end of study, will be recorded on case report forms (CRFs). Occurrences of atrial fibrillation and atrial flutter will be recorded and reported on as part of the efficacy assessment, and are not considered adverse events.

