Serious adverse events (SAEs) are events that place the participants health in jeopardy and that occur despite following all labeling precautions and instructions for use and where all attempts at correction by medical intervention do not resolve the event. All SAEs must be reported to the Ethics Committee (EC) within 48 hours of the investigator becoming aware of the SAE. Re-hospitalization for cardiovascular reasons is part of the primary endpoint and therefore does not qualify as an SAE.

An unanticipated adverse device effect (UADE) is defined as any SAE on health or safety, or any life-threatening problem or death caused by, or associated with, the device, if that effect, problem, or death was not previously identified in nature, severity, or degree of incidence in the investigational plan or application. An UADE is also defined as any other unanticipated serious problem associated with a device that relates to the rights, safety, or welfare of participants.

Should an UADE occur, the investigator is required to notify the EC as soon as possible, but in no event later than 10 working days after the investigator first learns of the event. An immediate evaluation of any UADE will be conducted. If there is significant new information that could affect the risk/benefit analysis as given in Section 7.1 of this protocol, the ECs will be informed and if appropriate, actions such as study hold, patient re-consent or study termination will be taken.

All participant deaths must be immediately reported to the EC (24 h upon investigators knowledge). When possible and permitted by family members, an autopsy shall be performed. The death certificate, coroner's report, and laboratory and autopsy reports, if available, should be provided to the EC.

10. Documentation

All patient data will be documented in CRFs. Personal data such as name, address, contact data etc. are excluded from the documentation in the eCRF. Names of all patients will be pseudomized and underlie national data protection laws. The principal investigator will conserve the patient identification list, the signed informed consent forms and the original data including the patient chart for 15 years.

11. Study organization

Principle Investigators: [name]. med. [name]
MVZ CCB Frankfurt und Main Taunus GbR
Am Agaplesion Markus Krankenhaus
[name]
[contact]
Fax: [name]
E-Mail: [contact]

Priv. Doz. Dr. med. [name]

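### Section 9 exempts every cardiovascular re-hospitalization from SAE status, with no exception for admissions caused by the ablation, the device or antiarrhythmic drugs

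*Protocol*

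**What the plan says.** Four parts of the protocol bear on this.

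- **Section 9 (Adverse Events), exemption.** "Re-hospitalization for cardiovascular reasons is part of the primary endpoint and therefore does not qualify as an SAE". No cause of admission is excepted.
- **Section 9, reporting.** "All SAEs must be reported to the Ethics Committee (EC) within 48 hours of the investigator becoming aware of the SAE". The same section defines an SAE narrowly, as an event that endangers health and that persists after every attempt to correct it medically.
- **Section 8 (Statistical Analysis), stopping.** The first trigger is "Occurrence of serious adverse events in more than 10% of the study population associated with the ablation procedure", followed by "Of note, re-hospitalization for cardiovascular reasons meets the primary study endpoint". A second rule reads "Occurrence of >10% major procedural complications defined as cardiac tamponade, stroke/TIA, air embolism, major bleeding the study has to be stopped", followed by "Of note re-hospitalization for cardiovascular reasons meets the primary endpoint".
- **Section 6 (Endpoints).** For the primary endpoint, the section says that it "is a composite of cardiovascular hospitalization (worsening heart failure, acute coronary syndrome, AF/AT recurrence, cardioversions, re-ablations), death, systemic embolism, stroke (ischemic, hemorrhagic". Cardiovascular care given as an emergency is the remaining component. The bracket after cardiovascular hospitalization does not name procedural complications.

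The Risk-Benefit-Analysis lists the complications expected from ablation. They begin with "Vascular access complications such as vascular damage, neural damage, hematoma, bleeding (approx. 2-3"%) and include tamponade, thrombo-embolic events and pulmonary vein stenosis or occlusion.

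**The concern.** Keeping expected disease events, such as AF recurrence, out of expedited reporting because they are already counted as endpoints can be defended. This sentence goes further. Several complications that the protocol itself expects from the ablation can bring a patient back to hospital for a cardiovascular reason, and the sentence exempts that admission as well. Being an efficacy event does not make an admission non-serious or unrelated to treatment.

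Participant protection is at stake, and so is the safety conclusion. A related re-admission would not reach the EC within 48 hours as an SAE, and the count that can stop the trial for ablation harm would be too low. Section 8 plans no interim analysis, so no scheduled look at the data would make up for it.

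**Working it through.** The protocol gives no figure to reproduce here. The check is mainly a reading of the sections side by side, followed by an illustration.

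**Step 1: what depends on SAE status.** The 48-hour EC report (section 9) and the first trigger (section 8) both count SAEs. An event without SAE status enters neither.

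**Step 2: which other routes remain for a related cardiovascular re-admission.**

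| Route | Where | What it still catches | What it leaves open |
|---|---|---|---|
| Second 10% rule | Section 8 | Tamponade, stroke/TIA, air embolism, major bleeding, whether or not they are SAEs | Pulmonary vein stenosis, non-bleeding vascular injury |
| CRF recording of all AEs | Section 9 | The event itself | No expedited report, no trigger |
| Death report within 24 h | Section 9 | Deaths | Non-fatal events |
| Unanticipated device effect | Section 9 | Effects not identified beforehand in nature, severity or incidence | In general, complications already listed in the Risk-Benefit-Analysis |
| Termination for an unknown complication or risk | Section 8 | New kinds of harm | Known complications |
| Secondary safety endpoint | Section 6 | Listed peri-procedural complications; stopping of AAD for side effects | No expedited report, no trigger |

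No route restores EC reporting within 48 hours, or a place in a stopping count, for a non-fatal re-admission due to pulmonary vein stenosis or a non-bleeding vascular injury.

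**Step 3: drug-related admissions.** The first trigger is confined to SAEs associated with the ablation procedure. Admissions caused by antiarrhythmic drugs were never part of it, so for them the loss is in SAE reporting only.

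**Step 4: illustration of the trigger.** The denominator is ambiguous. More than 10% means at least 11 if it is the 100 ablated patients, and at least 21 if the study population is all 200. Let p be the true share of ablated patients with an ablation-associated serious event, and f the share of these exempted as cardiovascular re-hospitalizations. The protocol gives neither, so both are assumptions. The counted events are binomial with n = 100 and probability p × (1 − f).

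| p | f | p × (1 − f) | P(at least 11 of 100) | P(at least 21 of 100) |
|---|---|---|---|---|
| 0.15 | 0 | 0.15 | 0.90 | 0.066 |
| 0.15 | 0.25 | 0.1125 | 0.58 | 0.0035 |
| 0.15 | 0.50 | 0.075 | 0.13 | <0.0001 |
| 0.20 | 0 | 0.20 | 0.99 | 0.44 |
| 0.20 | 0.25 | 0.15 | 0.90 | 0.066 |
| 0.20 | 0.50 | 0.10 | 0.42 | 0.0008 |

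**Step 5: the protocol's own rates.** The upper figures for vascular access, tamponade, thrombo-embolic and pulmonary vein complications sum to 3 + 1 + 1 + 0.5 = 5.5 per 100. At p = 0.055 with nothing exempted, P(at least 11 of 100) is about 0.02. At the expected rates the trigger would therefore rarely fire with or without the exemption. The exemption matters if harm is more frequent than expected, which is the situation a stopping rule is for.

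**The case against.** The strongest reply is that the sentence exempts the re-hospitalization, not the complication behind it. A late tamponade or stroke could still be an SAE in its own right. The endpoint bracket in section 6 also does not name pulmonary vein stenosis, groin injury or drug-induced bradycardia, so it is unclear whether these admissions are endpoint events, and hence whether the exemption reaches them. This stands as ambiguity. It does not remove the point: section 9 speaks of cardiovascular reasons in general, nothing in the text keeps related admissions in, and a site that follows the sentence literally would not report them.

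Four stronger readings may tempt a reader, and the protocol does not support them.

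- *The same complication is an SAE before index discharge and not after.* This is doubtful. The SAE definition already leaves out events that treatment resolves, so a drained tamponade or a repaired vessel may fail it during the index stay too.
- *Drug complications drop out of the stopping trigger.* They were never in it.
- *Late complications escape all oversight.* The remaining routes in the table above capture part of them.
- *The two notes in section 8 exclude re-admissions from the 10% counts.* They say only that such admissions meet the endpoint. They invite the exclusion but do not state it.

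**Conclusion.** The point holds in a limited form. As written, section 9 takes ablation-related, device-related and drug-related cardiovascular re-hospitalizations out of SAE status together with the unrelated ones. For ablation-related admissions, both the 48-hour EC report and the first 10% trigger are lost, unless the underlying event is separately judged an SAE. For drug-related admissions, only SAE reporting is lost. The clearest gap concerns complications outside the second 10% rule, such as pulmonary vein stenosis and non-bleeding vascular injury. Non-cardiovascular re-admissions are unaffected by this sentence.

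The size cannot be derived from the protocol, because it gives neither the true rate of serious ablation events nor the share that would present as a re-admission. The probabilities above are illustrations on assumed values. The direction does not depend on them: the exemption can only lower the count. The narrow SAE definition is a related but separate weakness. Correcting either one alone would leave the other in force.

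**What to change.** 1. **Section 9, exemption.** Limit it to cardiovascular re-hospitalizations judged unrelated to the procedure, the device or antiarrhythmic medication. Say that this includes unrelated AF/AT recurrence, cardioversion, re-ablation, worsening heart failure and acute coronary syndrome, so that every endpoint admission is classified.
2. **Section 9, principle.** State that endpoint status does not remove a related serious event from SAE reporting or, if it is ablation-related, from the section 8 trigger. Such an event is then both an endpoint event and an SAE.
3. **Section 9, SAE definition.** Reconcile it with items 1 and 2, so that a related re-admission is not excluded because treatment resolved it. Otherwise the new wording would contradict the definition.
4. **Section 8 and section 6.** Align the two notes beside the stopping rules, and make clear in the endpoint list whether an admission for a procedural complication is a primary-endpoint event. State at the same time whether the 10% refers to the ablated patients or to all 200.

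The cost is protocol wording, one relatedness field on the hospitalization CRF and a few more EC reports. Sample size, visits and treatment are unchanged.
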